6.7 Efficacy Analyses

Not applicable for this study.

6.8 Safety Analyses

Statistical methods for the safety analyses will be descriptive in nature and no formal statistical comparisons will be made. Endpoints will be summarised by treatment group and period based on the methods described in Section 5.1.

Safety endpoints will be analysed based on the Safety Analysis Set.

6.8.1 Exposure to Study Drug

All collected study drug administration data will be listed.

6.8.2 Adverse Events

All tables will present the number of subjects who experienced an AE (count and percentage) and the actual number of AEs (count only) within each specific category by treatment group and for all subjects overall. Subjects who experienced multiple AEs will only be counted once in each relevant category (high-level summary, SOC, PT, severity rating or relationship to study drug category), but all events will be included in the event counts. Percentages will be based on the number of subjects in the Safety Analysis Set. Tables will only include treatment-emergent events.

The overall summary of TEAEs table will present the total number of subjects who experienced a TEAE and the total number of TEAEs in each of the following categories:

- At least one TEAE.
- At least one serious TEAE.
- At least one severe TEAE.
- At least one treatment-related TEAE.
- At least one TEAE leading to the withdrawal of study drug.

Sponsor: BeiGene, Ltd.**Protocol Number:** BGB-Sitravatinib-101

- At least one TEAE leading to study withdrawal.

The summary of TEAEs table will include the number of subjects who experienced at least one TEAE and the corresponding number of events, and furthermore summarise the TEAE data by SOC and preferred term within SOCs. System organ class terms will be sorted alphabetically, and preferred terms will be sorted alphabetically within SOCs in the table.

The summary of SAEs table will include the number of subjects who experienced at least one SAE and the corresponding number of SAEs, and furthermore summarise the SAE data by SOC and preferred term within SOCs. System organ class terms will be sorted alphabetically, and preferred terms will be sorted alphabetically within SOCs in the table.

The summary of treatment-related TEAEs table will include the number of subjects who experienced at least one treatment-related TEAE and the corresponding number of events, and furthermore summarise the TEAE data by SOC and preferred term within SOCs. System organ class terms will be sorted alphabetically, and preferred terms will be sorted alphabetically within SOCs in the table.

The summary of TEAEs leading to study drug withdrawal table will include the number of subjects who experienced at least one TEAE that lead to the withdrawal of study drug and the corresponding number of events, and furthermore summarise the TEAE data by SOC and preferred term within SOCs. System organ class terms will be sorted alphabetically, and preferred terms will be sorted alphabetically within SOCs in the table.

The summary of TEAEs leading to study withdrawal table will include the number of subjects who experienced at least one TEAE that lead to study withdrawal and the corresponding number of events, and furthermore summarise the TEAE data by SOC and preferred term within SOCs. System organ class terms will be sorted alphabetically, and preferred terms will be sorted alphabetically within SOCs in the table.

The summary of TEAEs by severity table will include the number of subjects who experienced at least one TEAE, the number of subjects who experienced at least one TEAE within each severity rating ('Mild', 'Moderate', 'Severe', 'Life-threatening', 'Fatal') and the corresponding number of events for each rating. In addition, the TEAE data will be summarised by SOC, preferred term within SOC, and severity rating within preferred term. System organ class terms will be sorted alphabetically, preferred terms will be sorted alphabetically within SOCs and severity ratings will be sorted in increasing order of severity within preferred terms in the table.

The summary of TEAEs by relationship to study drug (causality) table will include the number of subjects who experienced at least one TEAE, the number of subjects who experienced at least one TEAE within each relationship category ('Related', 'Not Related') and the corresponding number of events for each category. In addition, the TEAE data will be summarised by SOC, preferred term within SOC, and relationship category within preferred term. System organ class terms will be sorted alphabetically, preferred terms will be sorted alphabetically within SOCs and relationship category will be sorted from the least to the most likely relationship to study drug within preferred terms in the table.

The listing of AEs will include all AE data in the clinical database. The listing will present all the information (fields) collected on the 'Adverse Event' CRF page, as well as the SOC and preferred terms obtained from the MedDRA dictionary. In addition, the AE period start and end days (relative to the study drug administration of the treatment group that the AE was assigned to) and a flag indicating whether the AE was treatment emergent will be presented. Non-TEAEs will be listed under the first treatment that a subject received. If the AE was ongoing at the end of the study, 'Ongoing' will be presented under the 'Stop Date/Stop Time/Study Day' heading. Partial dates/times will be presented as described in Section 5.1.4. The subsets of SAEs, treatment-related AEs, AEs leading to the withdrawal of study drug or withdrawal from the study will be listed separately and will include all the information presented in the main AE listing.

6.8.3 Laboratory Parameters

The laboratory parameters described in Section 4.1.3 will be summarised and listed.

The summary of hematology and biochemistry results tables will present summary statistics for each laboratory parameter within the specific test panel. For each parameter, summaries will be presented for the baseline and each scheduled post-baseline visit. In addition, summaries will be presented for the change from baseline values at each scheduled post-baseline visit. Refer to Section 4.1.3 for the handling of character results.

The summary of urinalysis result classification table will present summaries for the baseline and each scheduled post-baseline visit for each of the defined categories ('Normal' and 'Abnormal') within each urinalysis parameter.

The listings of hematology and biochemistry data will include all laboratory data (collected at scheduled and unscheduled visits) in the clinical database. The listings will present all the information (fields) that is available in the laboratory data set. In addition, the observation that was used as the baseline records (values) for each parameter will be flagged, the change from baseline value and the derived result classification (based on the normal ranges where applicable) at each post-baseline visit will be presented. A separate listing that includes only the subset of subjects that had at least one abnormal result will also be created for each test panel. All the subjects' results for every parameter where at least one abnormal classification was observed will be included.

The listing of urinalysis data will include all laboratory data (collected at scheduled and unscheduled visits) in the clinical database. The listings will present all the information (fields) that is available in the laboratory data set. In addition, the observation that was used as the baseline record (value) for each parameter will be flagged and the result classification (derived or based on the normal range where applicable) will be presented. A separate listing that includes only the subset of subjects that had at least one abnormal result will also be created. All the subjects' results for every parameter where at least one abnormal classification was observed will be included.

The listings of alcohol breath test results, urine drug screen and cotinine test, thyroid-stimulating hormone, SARS-CoV-2 test, serology and urine microscopy data will include all available results (collected at scheduled and unscheduled visits) in the clinical database. The listing will present all the information (fields) that is available in the laboratory data set.

6.8.4 Electrocardiogram (ECG) Parameters

The ECG parameters described in Section 4.1.4 will be summarised and listed.

The summary of ECG measurements tables will present summary statistics of the results at the baseline and each scheduled post-baseline visit/time point for each parameter. In addition, summaries will be presented for the change from baseline values (period baselines) at each scheduled post-baseline visit/time point.

The summary of ECG overall assessments tables will present table will present summaries for the baseline and each scheduled post-baseline visit/time point for each of the defined categories ('Normal', 'Abnormal NCS' and 'Abnormal CS').

The listings of ECG results will include all data (collected at scheduled and unscheduled visits) in the clinical database. Results will be listed per visit and scheduled time point, including the results, normal range values and the normal range indicator for each parameter. The observations that were used as the baseline records for each parameter will be flagged and the change from baseline values at each post-baseline visit/time point will be presented. The listing will also include the normal ranges for each parameter (where defined) and a normal range indicator.

6.8.5 Vital Signs

The vital signs parameters described in Section 4.1.5 will be summarised and listed.

The summary of vital signs results tables will present summary statistics for results at the baseline and each scheduled post-baseline visit/time point for each parameter. In addition, summaries will be

presented for the change from baseline values (period baselines) at each scheduled post-baseline visit/time point.

The listings of vital signs results will include all data (collected at scheduled and unscheduled visits) in the clinical database. The observations that were used as the baseline records for each parameter will be flagged and the change from baseline values at each post-baseline visit/time point will be presented. The listing will also include the normal ranges for each parameter (where defined), a normal range indicator and the clinical significance flags (if applicable) as reported by the Investigator.

6.8.6 Physical Examination

The physical examination assessment data described in Section 4.1.6 will be listed.

6.8.7 Fasting Status and Water Restrictions

The collected fasting status and water restriction information data described in Section 4.1.7 will be listed.

6.9 Pharmacokinetic Analyses

6.9.1 Plasma Concentrations

The analysis of the PK concentration data will be based on the PK Concentrations Analysis Set.

The plasma sitravatinib concentrations data will be summarised by treatment group and nominal collection time points using the statistics described in Section 5.1.3. BLQ concentrations that occurred prior to C_{max} will be set to 0, and treated as missing otherwise, for the calculation of summary statistics. Zero values will be treated as missing for the calculation of the geometric statistics. Missing values will be omitted from the calculation of descriptive statistics.

Figures of the individual plasma concentrations vs. actual time profiles (both treatment groups for each subject on the same plot) will be presented on a linear and a log-linear scale. All concentration for both treatment groups will also be presented in the same spaghetti plot presented on a linear and a log-linear scale. BLQ concentrations that occurred prior to C_{max} will be set to 0 and treated as missing otherwise in the linear plots. BLQ concentrations will be set to missing in the log-linear plots.

Mean concentration profiles vs. nominal time curves will be presented on a linear and log-linear scale. Both treatment groups will be presented on the same plot. Standard deviation bars will also be presented.

All plasma concentration data will be listed, and the listing will include the calculated elapsed time since the study drug administration in the specific period and the time deviations between the actual and planned sample collection times.

6.9.2 Pharmacokinetic Parameters

The calculated plasma PK parameters described in Section 4.3 will be summarised by treatment group using the statistics described in Section 5.1.3. The summary tables will be based on the PK Parameters Analysis Set.

Relative bioavailability will be summarised separately based on the Relative Bioavailability Analysis Set.

The analysis of the relative bioavailability between the two different formulations of sitravatinib (sitravatinib MSC as test and sitravatinib FBC as reference) will be based on the dose-dependent parameters AUC_{0-inf} , AUC_{0-t} and C_{max} . The \log_e -transformed parameters will be analyzed separately using a mixed effect model (data permitting) with the treatment group (formulation), sequence and period as fixed effects and subject nested within sequence as a random effect. The geometric means (exponentiated least squares means) and the associated 90% confidence intervals for each treatment group and the geometric mean ratio (exponentiated difference between sitravatinib MSC least-squares mean as test and sitravatinib FBC least-squares mean as reference) and the associated 90% confidence interval will be presented. The geometric mean ratios and the associated confidence

Sponsor: BeiGene, Ltd.

Protocol Number: BGB-Sitravatinib-101

intervals will be expressed as percentages. Bioequivalence will be concluded if the 90% confidence intervals of the geometric mean ratios of all three parameters lies entirely within the bioequivalence interval of 80% to 125%. Refer to Appendix 3 for the SAS® code that will be used for the analysis. The analysis will be based on the Relative Bioavailability Analysis Set.

The analysis will also be repeated based on the dose-normalized AUC_{0-inf} , AUC_{0-t} and C_{max} results.

The parameters AUC_{0-inf} , AUC_{0-t} and C_{max} will also be presented graphically by means of box-and-whiskers plots. The results for the two treatment groups will be presented on the same plot. The dose-normalized AUC_{0-inf} , AUC_{0-t} and C_{max} results will also be plotted separately. The plots will be based on the Relative Bioavailability Analysis Set.

All parameter results will be listed based on the PK Parameters Analysis Set, and any results that may have been excluded from the summary tables will be flagged. The SAS® outputs generated by the respective models will be presented in listings.

7. Changes to the Planned Analyses

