8. SAMPLE SIZE AND DATA ANALYSIS

8.1. Determination of Sample Size

Up to 26 subjects (13 per dosing sequence) will be enrolled to guarantee that at least 24 subjects complete the study. The number of subjects is justified in powering the study to delineate comparability of the sitratavinib mean exposure between the 2 dose formulations. Assuming an intra-subject coefficient of variation (CV%) of 40% (which was the maximum CV% observed on C_{\max} in previous study), and a malate salt capsule to free base ratio of $100 \pm 5\%$, 24 subjects in a 2-way crossover design will provide a probability of 92% for the ratio of geometric means (malate salt to free base) to be within the 80% to 125% limits if the true ratio is between 95% and 105%. The conclusions in the clinical study report will be drawn based on the estimated ratios of geometric means only and the 90% confidence intervals (CIs) will be presented for informational purposes.

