8.3. Pharmacokinetic Analyses

The plasma PK parameters of sitratavinib will be calculated using standard noncompartmental methods, based on actual sample collection time rather than scheduled times.

For the analysis of relative bioavailability between sitratavinib malate salt (test) and sitratavinib free base (reference), log-transformed PK parameters ($AUC_{0-\infty}$, AUC_{0-t} , and C_{\max}) for sitratavinib will be analyzed by a mixed effect model. This model will include formulation, period, and sequence as fixed effects and subject as a random effect.

For PK parameters ($AUC_{0-\infty}$, AUC_{0-t} , and C_{\max}) for sitratavinib, a point estimate and its associated 90% CI will be constructed for the difference between test and reference capsules and this difference and its 90% CI will be exponentiated to obtain the estimate of the ratio of geometric least-squares means and its 90% CI. The ratio of test formulation to reference formulation will be calculated on both non-dose-normalized and dose-normalized PK parameters. Estimated geometric means will also be presented by each formulation.

All other PK parameters will not be subject to inferential statistical analysis and only descriptive statistics (n, arithmetic mean, standard deviation, arithmetic CV, geometric mean, geometric CV, median, min, max, as appropriate) will be presented for them.

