2.4 Sample Size Determination

Up to 26 subjects (13 per dosing sequence) will be enrolled to guarantee that at least 24 subjects complete the study. The number of subjects is justified in powering the study to delineate comparability of the sitravatinib mean exposure between the two dose formulations. Assuming an intrasubject coefficient of variation (CV%) of 40% (which was the maximum CV% observed on C_{max} in previous study), and a malate salt capsule to free base ratio of $100 \pm 5\%$, 24 subjects in a two-way crossover design will provide a probability of 92% for the ratio of geometric means (malate salt to free base) to be within the 80% to 125% limits if the true ratio is between 95% and 105%. The conclusions in the clinical study report will be drawn based on the estimated ratios of geometric means only and the 90% confidence intervals (CIs) will be presented for informational purposes.

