5.2 Hypotheses and Decision Rules

Not applicable.

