7.1 Changes to the Analyses Described in the Study Protocol and Protocol Amendments

No changes were made to the analyses described in the study protocol.

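### SAP 6.9.2 concludes bioequivalence from 90% confidence intervals, while Protocol 8.1 and SAP 2.4 rest conclusions on point estimates; the stated 92% does not apply to the interval rule

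*SAP*

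**What the plan says.** Four statements bear on how the primary pharmacokinetic comparison is to be concluded.

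- **Protocol 8.1**, repeated in SAP 2.4: the study report's conclusions are to be "drawn based on the estimated ratios of geometric means only and the 90% confidence intervals (CIs) will be presented for informational purposes".
- **SAP 6.9.2**: "Bioequivalence will be concluded if the 90% confidence intervals of the geometric mean ratios of all three parameters lies entirely within" 80% to 125%. The three parameters are AUC0-inf, AUC0-t and Cmax.
- **SAP "5.2 Hypotheses and Decision Rules"**: the entry is that this is not applicable.
- **SAP 7.1**: "No changes were made to the analyses described in the study protocol".

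The protocol's own analysis text (Synopsis and 8.3) asks for the ratio and its 90% confidence interval and contains no bioequivalence criterion.

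The sample-size statement in SAP 2.4, matching Protocol 8.1, is that "24 subjects in a two-way crossover design will provide a probability of 92% for the ratio of geometric means" to lie within 80% to 125% when the true ratio is 95% to 105%. It rests on this input: "Assuming an intra-subject coefficient of variation (CV%) of 40% (which was the maximum CV% observed on" Cmax in an earlier study).

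Protocol 8.3 adds: "The ratio of test formulation to reference formulation will be calculated on both non-dose-normalized and dose-normalized PK parameters". SAP 6.9.2 likewise repeats the analysis on dose-normalized values, straight after stating the 80% to 125% rule.

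**The concern.** A confidence interval cannot be both informational and decisive. The conflict runs between the SAP and the protocol, and also inside the SAP, between 2.4 and 6.9.2. The two places that should settle it do not: SAP 5.2 says there is no decision rule, and SAP 7.1 says nothing was changed.

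Two things are at stake. First, the basis of the primary conclusion could be chosen after the results are known, because both readings are in writing. Second, the only probability of success in the plan belongs to the point-estimate reading. Anyone who sets the 92% beside the 6.9.2 criterion gets a badly wrong idea of how likely that criterion is to be met.

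**Working it through.** **Inputs from the documents.** Intra-subject CV 40%; 24 completers in a 2×2 crossover with 1:1 allocation; limits 0.80 to 1.25; true ratio r from 0.95 to 1.05 (Protocol 8.1, SAP 2.4); 90% intervals (SAP 6.9.2 and Appendix 3).

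**Standard error.** Log-scale within-subject SD = √ln(1 + 0.40²) = 0.3853. SE of the log ratio = 0.3853 × √(2/24) = 0.1112.

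**Reproducing the 92%: point estimate within the limits.**
P = Φ[(ln 1.25 − ln r)/SE] − Φ[(ln 0.80 − ln r)/SE].
At r = 0.95 this is Φ(2.468) − Φ(−1.545) = 93.2%. If the CV is used directly as the SD (0.40), it is 92.3%. So the stated 92% reproduces as the probability for one parameter's point estimate.

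**The SAP 6.9.2 rule, one parameter.** The half-width is t(0.95; 22) × estimated SE, with t = 1.717. The probability that the whole interval lies within the limits was integrated over the chi-square distribution of the residual variance (22 df). A simulation of 1,000,000 trials per ratio agreed. An interval inside the limits implies a point estimate inside them, so the share of trials that pass the first criterion and fail the second is the difference.

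| True ratio | Point estimate within limits | 90% CI within limits | First met, second failed |
|---|---|---|---|
| 0.95 | 93.2% | 22.5% | 70.7% |
| 1.00 | 95.5% | 24.8% | 70.7% |
| 1.05 | 93.4% | 22.7% | 70.7% |

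The reason is the interval width. If the residual SD equals its planning value, the half-width is 1.717 × 0.1112 = 0.191 on the log scale, so the observed ratio would have to lie between about 0.968 and 1.033.

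**Sensitivity.**

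- All 26 subjects complete, CV 40%: interval rule 27.4 / 30.4 / 27.7% at r = 0.95 / 1.00 / 1.05.
- SD taken as 0.40, n = 24: interval rule 18.4 / 20.1 / 18.5%.
- Lower CV, n = 24, r = 0.95:

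| CV | 90% CI within limits | Point estimate in, CI not |
|---|---|---|
| 35% | 38% | 58% |
| 30% | 56% | 42% |
| 25% | 74% | 25% |
| 20% | 90% | 10% |

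- With n = 24, the interval rule reaches 80% only at a CV of about 23% or less (r = 0.95) or 26% or less (r = 1.00).
- Completers needed for 80% under the interval rule, at r = 0.95 / 1.00 / 1.05: 66 / 54 / 64 at CV 40%; 40 / 32 / 38 at CV 30%; 28 / 24 / 28 at CV 25%.

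**All three parameters together.** The documents give no AUC CVs and no between-parameter correlations, so these figures rest on assumptions: r = 0.95, correlations 0.5 to 0.95, 200,000 simulated trials per setting. With every CV at 40%, all three point estimates fall within the limits in 84% to 91% of trials and all three intervals in 2% to 12%. With Cmax at 40% and both AUCs at 25%, the figures are 92% to 93% and 16% to 23%.

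**Dose-normalized scale.** Dividing by 100 mg (test) and 120 mg (reference) multiplies the ratio by 120/100 = 1.2. A raw ratio of 1.00 becomes 1.20, and 1.05 becomes 1.26, outside the limits. Limits of 0.80 to 1.25 on that scale correspond to raw ratios of 0.80/1.2 = 0.667 to 1.25/1.2 = 1.042. The two scales therefore cannot share one 80% to 125% criterion.

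**The case against.** The strongest reply is that one stray sentence is being made to carry too much. Bioequivalence is neither an objective nor an endpoint. The aim is relative bioavailability, and the ratio is meant to guide dose. Protocol 8.1, SAP 2.4, SAP 5.2 and SAP 7.1 agree with one another, and only SAP 6.9.2 departs. The model, the ratios and the intervals reported would be identical either way. The 92% is right for the event it describes, and the sentence after it says the intervals are informational. Protocol 8.1 also never says outright that comparability is concluded when the point estimate is within 80% to 125%, so the 71% compares the SAP rule with the sample-size event, not with a stated decision rule. Finally, 40% is the largest CV seen, and on Cmax only.

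Much of this is fair. The 92% is not an arithmetic error, the estimates do not change, and the figures at CV 40% are the unfavourable end. But 6.9.2 is the section that governs the primary analysis, it does not label its rule secondary or exploratory, and nothing in the SAP subordinates it to 2.4. The textual conflict exists at any CV. Even at CV 25% and a true ratio of 0.95, about a quarter of trials would have a point estimate within the limits and still fail the interval rule for that parameter.

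**Conclusion.** The concern holds and should be corrected before the analysis. SAP 6.9.2 adds a bioequivalence rule that contradicts Protocol 8.1 and SAP 2.4, is not recognised in SAP 5.2, and is not declared in SAP 7.1. The stated 92% does not describe it. At the plan's own values the rule succeeds in about 22% to 25% of trials for a single parameter, which is an upper bound for all three when that parameter is Cmax at CV 40%. This uses the log-scale SD of 0.3853; reading the CV directly as the SD gives 18% to 20%. The contradiction depends on no assumption. The size of the power gap depends on the CV, and the three-parameter figures also depend on AUC variability and correlations that the documents do not give.

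**What to change.** **Preferred.** Delete the bioequivalence sentence from SAP 6.9.2. Conclusions then rest on the estimated ratios with descriptive 90% intervals, as in Protocol 8.1, and no bioequivalence conclusion is drawn. SAP 5.2 and 7.1 can stand as written. This takes one deleted sentence and no extra subjects; the sponsor gives up a formal bioequivalence claim.

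**If the interval rule is intended.** State it in SAP 5.2 and declare it in SAP 7.1 as a change from the protocol. Amend Protocol 8.1 and SAP 2.4 to say that the 92% does not apply to it, that its power at CV 40% is about 22% to 25% for one parameter and no higher for all three, and either why 24 completers are still accepted or what number replaces them. The cost is a protocol amendment and either openly low power at CV 40% or about 54 to 66 completers for 80% power on one parameter.

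**In either case.** Add one clause saying that any comparison with 80% to 125% refers to the ratios that are not dose-normalized. The dose-normalized analysis required by Protocol 8.3 can remain as a descriptive result.
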